Subjects will remain on a daily fixed dose throughout the initial 6-month treatment period. Subjects in each cohort continue to receive daily dosing (Cohort 1, 2.5 µg/kg; Cohort 2, up to 7.5 µg/kg, Cohort 3, up to 15 µg/kg, and Cohort 4, 30 µg/kg) for 6 months unless stopping criteria are met. When clinical safety is established and stopping criteria are not met after all 8-10 subjects have completed at minimum their first

10 days of cohort dosing, and after DMC review and approval, the subsequent cohort may be open to enrollment.

In the 18-month optional, open-label extension period, eligible Cohorts 1 and 2 subjects were dose escalated to the 15µg/kg dose while Cohort 3 and Cohort 4 subjects continued at their respective starting doses of 15µg/kg and 30µg/kg, respectively, based on the pre-specified dose adjustment criteria described in the protocol and amendments.

Figure 2.2.1: Study Design

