3.2 Data and Cohort Presentation

All available data for study BMN111-202 will be used for the final analysis. Efficacy data collected in study BMN111-901 that is 12 months prior to screening in BMN111-202 for subjects who subsequently enrolled in study BMN11-202, and are included in the corresponding analysis population, will be summarized in efficacy tables and figures.

For the initial 6-month period, unless otherwise specified, all data will be presented for each cohort and all cohorts combined.

In the extension period, efficacy and imaging assessment data will be summarized for Cohorts 1 and 2 subjects who switched to 15 μ g/kg by cohort, and Cohort 1 and 2 combined.

In the entire study period, efficacy and imaging assessment data will be summarized for Cohort 3 and Cohort 4 separately, and Cohort 3 and 4 combined.

In the extension period, all other data will be summarized by dose level and all cohorts combined. For the entire study period, unless otherwise specified, safety data are summarized by dose level, and by cohort, and all cohorts combined. Subjects in Cohorts 1 and 2 may be represented at multiple dose levels and are accounted once for each dose level they receive.

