10 COMPLIANCE

Treatment compliance will be calculated based on the drug exposure records captured in eCRF and summarized for the safety analysis population.

The total amount of study drug taken will be calculated from the data collected on the drug dispensation CRF during the study. The total planned study drug intake (planned dose) will be calculated as the doses planned in corresponding treatment duration.

Percentage compliance will be derived from the total amount of study drug intake divided by the planned study drug intake, and multiplied by 100%:

$$\text{Treatment Compliance} = 100 \times \frac{\text{Total Drug Taken}}{\text{Total Planned dose}}$$

, where planned dose is the protocol-specified dose which changes when subjects change/switch dose, and total drug taken takes into account any units left in the syringe.

Treatment compliance will be calculated and summarized by cohort and overall in the initial 6-month period. In the extension period, it will be calculated for each dose level a patient has ever taken and summarized by dose level for all cohorts combined. In the entire study period, it will be summarized by dose level for all cohorts combined, and by cohort and overall.

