11 EXTENT OF EXPOSURE TO STUDY DRUG

For each of the initial 6-month, the extension period, and entire study period, total duration of study drug exposure, mean daily dose received ($\mu\text{g}/\text{kg}$), number of subjects who missed at least one dose, and number of days subjects missed at least one dose (for subjects who missed at least one dose) will be presented using descriptive statistics such as n, mean, SD, median, minimum, and maximum.

The number and percentage of subjects who permanently discontinue study drug during the initial 6-month period, the extension period, and entire study period will be provided along with the reason for study drug discontinuation.

The summaries will be presented for each cohort and overall in the initial 6-month period by dose level in for the extension period, and by dose level, by cohort, and all cohorts combined. [REDACTED]

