For Cohort 1 and 2 subjects who were switched to 15µg/kg dose level, the endpoints will be summarized by descriptive statistics at -12M, -6M, Baseline, Day 183, the first visit a patient was switched to 15µg/kg as well as the first visit with at least 6 months, and 12 months on 15µg/kg per cohort, and Cohort 1 and 2 combined. Absolute measures and changes from baseline, or change from first visit a patient was switched to 15µg/kg (as applicable), are provided. It is important to note that since the time when the subjects switched doses differs the interpretation of the summaries of data for subjects who switch should be considered with caution.

For all parameters, figures by cohort summarizing the means and SDs are provided for the visits included in the summary tables.

Exploratory testing

P-values and 95% confidence intervals for the change between baseline and the post-treatment assessment (i.e. calculated as post-treatment-baseline) will be provided for the endpoints AGV, height Z-score and body proportions at the Month 6, Month 12, Month 18 and Month 24 visits. No testing is performed for the cohort 1 and 2 switcher assessments.

All p-values will be considered descriptive and no adjustment for multiplicity will be made.

The p-values are derived from the two-sided paired t-test on the following pair of hypotheses:

H0: Change from baseline = 0

H1: Change from baseline ≠ 0

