14 SAFETY EVALUATIONS

Safety analysis will be carried out for the initial 6-month period, the extension period, and the entire study period, respectively. For each of the periods, all subjects who receive at least one dose of study treatment in the corresponding period and have any post-treatment safety information will be included in the safety analysis. Safety will be assessed by examining the incidence, severity grade, and relationship to study drug of all treatment-emergent adverse events (TEAEs) reported during the study period. In addition, all other safety measures including clinical laboratory results, vital signs, electrocardiogram (ECG) and Echocardiogram (ECHO) values will be assessed. Unless otherwise specified, the baseline for safety endpoints is defined as the last non-missing assessment prior to the first dose. Numeric parameters will be summarized by descriptive statistics including n, mean, SD, median, minimum, and maximum. Adverse events will be summarized by number and percentage. Change from baseline will be calculated when both baseline and post-baseline results are non-missing numeric values.

For the initial 6-month period, unless otherwise specified, safety data will be presented for each cohort and all cohorts combined.

For the extension period, unless otherwise specified, safety data are summarized by dose level and all cohorts combined.

For the entire study period, unless otherwise specified, safety data are summarized by dose level and by cohort and all cohorts combined.

Subjects in Cohorts 1 and 2 may be represented at multiple dose levels and accounted once for each dose level they receive. Note the following rules are applied to associate the safety measure to a specific dose:

- AEs are associated to the dose taken on the start date of the AE.
- For mean summaries of safety parameters at visits over the course of the study the assessments on the day of escalation will be summarized under the previous dose.
- For mean summaries assessing pre and post dose measure on a specific day the assessments on the day of escalation will be summarized under the new dose.

For all summary tables for patients who discontinue treatment, all safety assessments within 30 days from the treatment discontinuation date will be included in summary tables.

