14.1 Adverse Events

Adverse events will be coded in accordance with MedDRA version 19.1. A TEAE is defined as any AE that newly appeared or worsened in severity following initiation of study drug administration during the AE reporting period. After informed consent is obtained and the first administration of study drug, all non-serious AEs and SAEs reporting period begins and continues until 4 weeks following either the last administration of study drug or the early termination visit, whichever is longer. If the onset date or end date of an adverse event is partial, the same imputation rules described in Section 9 will be applied.

AEs are summarized by incidence rates and for specific tables also by exposure adjusted incidence rates:

- Incidence rates calculated as number of subjects with the event divided by the number of subjects in the population being assessed
- Exposure-adjusted incidence rates (EAIR) are calculated by dividing the total number of events by the total treatment exposure in the period under assessment for the subjects in the population being assessed. The exposure time for each subject is derived as the time from the date of first dose, to the date of the last dose in the period under assessment.

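### Dose-level exposure-adjusted AE rates divide events on one dose by a switcher's exposure on all doses, so the 2.5, 7.5 and 15 µg/kg rates come out too low

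*SAP*

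**What the plan says.** Four rules act together on the same tables.

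- **Numerator.** SAP 14: "AEs are associated to the dose taken on the start date of the AE".
- **Columns.** SAP 14: "For the extension period, unless otherwise specified, safety data are summarized by dose level and all cohorts combined". Entire-study safety tables are shown by dose level, by cohort and combined. SAP 3.2 adds: "Subjects in Cohorts 1 and 2 may be represented at multiple dose levels and are accounted once for each dose level they receive".
- **Denominator.** SAP 14.1 divides total events by total treatment exposure of the subjects assessed. Each subject's exposure is "derived as the time from the date of first dose, to the date of the last dose in the period under assessment". The periods named in SAP 14 are the initial 6 months, the extension and the entire study.
- **Who switched.** SAP 2.2 reports that "eligible Cohorts 1 and 2 subjects were dose escalated to the" 15 µg/kg dose, while Cohorts 3 and 4 stayed on 15 and 30 µg/kg. SAP 12 asks for caution with switcher summaries "since the time when the subjects switched doses differs".

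Elsewhere the SAP does work by dose level. On extension-period compliance, SAP 10 says: "In the extension period, it will be calculated for each dose level a patient has ever taken". SAP 11 presents exposure "by dose level in for the extension period, and by dose level, by cohort, and all cohorts combined". SAP 14.1 refers to neither section.

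**The concern.** The numerator is specific to a dose and the denominator is not. A subject who spends nine months on 2.5 µg/kg and fifteen on 15 µg/kg adds 24 months to both columns, while the events are divided between them. Each affected rate is multiplied by time on dose over whole-period exposure, a factor that cannot exceed 1. The 30 µg/kg column has no planned switchers and keeps its full rate, so the comparison across doses is distorted and a dose-response can appear where there is none.

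Safety and tolerability is the primary objective. EAIR is used in 7 of the 17 AE summaries visible in SAP 14.1.1: all TEAEs, hypotension, events suggestive of hypotension, heart rate change, two on hypersensitivity, and injection site reactions. The entire-study tables also carry by-cohort columns, which are free of this error. The extension tables are planned only by dose level and combined, so they offer no such check.

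A smaller gap lies in the numerator: the SAP does not say which dose column receives an AE that starts on a day without a dose, such as a missed dose or the follow-up after the last one.

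**Working it through.** The documents give no EAIR, exposure total or switch date, so there is no figure to reproduce. The check is person-time arithmetic.

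**Inputs from the documents.** Planned sizes are 8 in Cohort 1, 8 in Cohort 2, and 8–10 in each of Cohorts 3 and 4 (SAP 2.2). Treatment lasts 6 + 18 = 24 months (protocol synopsis).

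**Assumptions.** All 16 Cohort 1 and 2 subjects move directly to 15 µg/kg at month *s*; everyone completes 24 months; Cohort 4 stays on 30 µg/kg; the AE rate is constant; for the extension, first dose means first dose in that period.

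**Formula.** Factor = (subject-months on the dose) / (subject-months under the SAP 14.1 rule). Write n₃ for the size of Cohort 3.

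- Entire study, 2.5 or 7.5 µg/kg: 8*s* / (8 × 24).
- Entire study, 15 µg/kg: [24n₃ + 16(24 − *s*)] / [24(n₃ + 16)].
- Extension, 2.5 or 7.5 µg/kg: (*s* − 6) / 18.
- Extension, 15 µg/kg: [18n₃ + 16(24 − *s*)] / [18(n₃ + 16)].
- 30 µg/kg: 1.00 throughout.

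**Entire study**

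| Switch | 2.5 and 7.5 | 15, n₃ = 8 | 15, n₃ = 10 | 30 |
|---|---|---|---|---|
| Month 6 | 48/192 = 0.25 | 480/576 = 0.83 | 528/624 = 0.85 | 1.00 |
| Month 9 | 72/192 = 0.38 | 432/576 = 0.75 | 480/624 = 0.77 | 1.00 |
| Month 12 | 96/192 = 0.50 | 384/576 = 0.67 | 432/624 = 0.69 | 1.00 |
| Month 18 | 144/192 = 0.75 | 288/576 = 0.50 | 336/624 = 0.54 | 1.00 |

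Up to month 12 the pattern rises with dose. At month 18 it is distorted but not monotone.

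**Extension only**

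| Switch | 2.5 and 7.5 | 15, n₃ = 8 | 15, n₃ = 10 | 30 |
|---|---|---|---|---|
| Month 6 | no time on dose | 432/432 = 1.00 | 468/468 = 1.00 | 1.00 |
| Month 9 | 3/18 = 0.17 | 384/432 = 0.89 | 420/468 = 0.90 | 1.00 |
| Month 12 | 6/18 = 0.33 | 336/432 = 0.78 | 372/468 = 0.79 | 1.00 |

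**Cross-check.** With cohorts of 8, 8, 10 and 10, the entire-study dose columns hold 192 + 192 + 624 + 240 = 1248 subject-months, against 36 × 24 = 864 actually accrued.

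**What splitting exposure does not cure.** Suppose there is no dose effect, but the AE rate is 5 in months 0–6 and 1 afterwards, with a month-6 switch and n₃ = 10. A 24-month subject has 5 × 6 + 1 × 18 = 48 events.

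| | 2.5 and 7.5 | 15 | 30 |
|---|---|---|---|
| Events | 30 per subject | 10 × 48 + 16 × 18 = 768 | 48 per subject |
| Rule as written | 30/24 = 1.25 | 768/624 = 1.23 | 48/24 = 2.00 |
| Exposure split by dose | 30/6 = 5.00 | 768/528 = 1.45 | 48/24 = 2.00 |

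By cohort, the rate is 48/24 = 2.00 in all four. Dose remains confounded with time on treatment, which is why the by-cohort rates must stand beside the dose-level ones.

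**The case against.** The best counter-argument is that the SAP should be read as a whole. SAP 11 presents duration of exposure by dose level, which makes little sense for switchers unless their time is split, and SAP 10 works per dose level. A sensible programmer could take the period under assessment to mean time on each dose, and the table specifications, which were not available, may say so. That may be how the tables are programmed. But SAP 14.1 gives its own explicit exposure rule, cites neither section, and relies on periods that SAP 14 defines as study phases. Followed exactly, it gives the wrong denominator.

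Several other points stand in part:

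- **Not everyone need switch.** SAP 2.2 says only eligible subjects did. If 6 of 8 switch at month 9 and 2 stop at month 6, the entire-study low-dose factor is (54 + 12)/(144 + 12) = 66/156 = 0.42. If those 2 instead stay on the low dose to month 24, it is (54 + 48)/192 = 0.53. The error shrinks but remains.
- **Extreme rows.** A month-18 switch for all is unlikely, since SAP 12 plans summaries at 12 months on 15 µg/kg. A month-6 switch for all is also unlikely: SAP 12 lists the first 15 µg/kg visit separately from Day 183, and protocol 9.1 requires cohort-wide review and at least 6 months of tolerability at intermediate doses.
- **30 µg/kg.** The protocol allows dose reductions, so its factor of 1.00 is an assumption.
- **Limited impact.** The summaries are descriptive, crude incidence appears beside each EAIR, and by-cohort rates are planned for the entire study.
- **Splitting alone can mislead.** The front-loaded example shows this, so it supports adding by-cohort rates rather than keeping the present rule.

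**Conclusion.** The concern holds. As written, the dose-level EAIRs are understated wherever a subject changes dose within the period. The direction is certain; the size depends on undisclosed switch dates. For switches between months 6 and 12, and under the stated assumptions, entire-study rates are reported at 0.25–0.50 of the dose-specific rate for 2.5 and 7.5 µg/kg and at 0.67–0.85 for 15 µg/kg, with 30 µg/kg unchanged. In the extension there is no error for a switch exactly at its start; for switches at months 9 to 12 the factors are 0.17–0.33 and 0.78–0.90. Initial-period tables, by-cohort and combined columns, and crude incidence are not affected. The point should be fixed because it concerns the primary objective and the special-interest events, but no formal test in the SAP depends on it.

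**What to change.** - **SAP 14.1.** State that in dose-level columns each subject's exposure is the sum of days assigned to that dose level within the period, split at every dose change, including any re-challenge at a lower dose. Count the escalation day under the dose taken that day, to match the AE rule. Make clear that for the extension the first dose means the first extension dose.
- **SAP 14.** Assign an AE that starts on an undosed day to the most recent dose level administered on or before onset.
- **Tables.** Show by-cohort EAIRs beside the dose-level EAIRs. They are already planned for the entire study and need adding for the extension.
- **Footnote.** State that in switchers dose is confounded with time on treatment.

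The cost is a few sentences of SAP text, one footnote, and reprogramming of seven summaries in two affected periods, so 7 × 2 = 14 outputs. Protocol 9.4.4 already requires the date, volume and concentration of each dose to be recorded, so no new data are needed.

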14.1.1 All Adverse Events

The following summaries will be provided for each period:

- Overall Summary of AEs
- TEAEs by System Organ Class (SOC), Preferred Term (PT), and severity
- TEAEs assessed by investigators as related to study drug by SOC, PT and severity
- TEAEs by PT
- TEAEs by SOC
- Serious AEs (SAEs) by SOC and PT
- TEAEs leading to discontinuation by PT
- Incidence and exposure-adjusted event rates of TEAEs by SOC and PT

[figure not shown]
AEs of Special Interest

- Injection site reactions by SOC, PT, and severity
- Frequency and duration of ISRs
- ISR symptom by SOC, PT and severity
- Incidence and exposure-adjusted event rates of Hypotension TEAEs by SOC and PT
- Incidence and exposure-adjusted event rates of Heart Rate Change TEAEs by SOC and PT
- Incidence and exposure-adjusted event rates of events suggestive of Hypotension TEAEs by SOC and PT
- Incidence and exposure-adjusted event rates of Hypersensitivity TEAEs (SMQ) by SOC and PT
- Incidence and exposure-adjusted event rates of Hypersensitivity TEAEs (excluding ISRs) by SOC and PT
- Incidence and exposure-adjusted event rates of ISRs TEAEs by SOC and PT

Search criteria for the ADR/SMQ search criteria:

- Injection Site Reaction (ISR)
 - TEAEs are identified using having high level terms of MedDRA of ‘Injection Site Reaction’
 - ISR Symptom page, which captures additional symptoms associated with a specific ISR AE
- Hypotension
 - TEAEs are identified as PT: Blood pressure ambulatory decreased, Blood pressure decreased, Blood pressure diastolic decreased, Blood pressure orthostatic decreased, Blood pressure systolic decreased, Blood pressure systolic inspiratory decreased, Diastolic hypotension, Hypotension, Orthostatic hypotension
 - TEAEs suggestive of Hypotension are identified as PT: Fatigue, Nausea, Loss of consciousness, Vision blurred, Cold sweat, Dizziness, Syncope, Presyncope.
- Heart Rate Change
 - TEAEs of Heart Rate Change are identified as PT: Atrial tachycardia, Postural orthostatic tachycardia syndrome, Rebound tachycardia, Sinus tachycardia, Supraventricular tachycardia, Tachycardia, Tachycardia paroxysmal, Ventricular tachycardia, Bradycardia.
- Hypersensitivity – refer to BioMarin pharmacovigilance standard search terms
 - TEAEs – Broad Hypersensitivity SMQ (421 narrow and broad search term PTs)
 - [REDACTED]

A figure is provided for Mean Frequency of Injection Site Reactions by Month in Entire Study Period for all Cohorts by Dose

■ [REDACTED]

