7.4 Summary of Overall Risks and Benefits

7.4.1 Summary of Risks from Nonclinical Studies

7.4.2 Summary of Risks from Clinical Studies

7.4.2.1 111-101

Based on review of the first-in-human Phase 1 study of BMN 111 in healthy adult volunteers, Study 111-101, BMN 111 administered SC daily was well tolerated with doses ranging from 0.5 µg/kg to 15 µg/kg. All AEs were of mild severity, and no SAEs were reported. The most common AE was mild, transient, self-limited orthostatic hypotension, of which the majority of cases were asymptomatic and observed only upon assumption of an upright posture following recumbence. No dose-limiting toxicities were identified outside of these CV findings.

7.4.2.2 111-202

Based on review of this ongoing phase 2 clinical trial, injection site reactions have been identified as risks associated with BMN 111 injections. Hypotension and hypersensitivity reactions are potential risks associated with BMN 111 injections. For a detailed summary of risks, please refer to the current IB.

	BMN 111-202 Amendment 4	Page 32
---	-------------------------	---------

In the phase 2 study BMN 111-202, injection site reactions were the most common AEs reported and are considered as an identified risk associated with BMN 111 injections. The most common injection site reactions across all cohorts included: injection site erythema, injection site swelling, and injection site urticaria. Of note, all injection site reactions have been reported as non-serious and grade 1 in severity, and no subjects have discontinued from the study or permanently discontinued study treatment as a result of the events.

The most important potential risks identified to date include hypotension (and complications related to hypotension and/or tachycardia) and the development of anti-BMN 111 antibodies. Anti-BMN 111 antibodies have the potential to mediate allergic reactions, reduce efficacy, and/or cross-react with endogenous CNP or other undefined agents. Anti-BMN 111 antibodies continue to be monitored in the study. No grade 2 or higher or serious hypersensitivity reactions have been reported to date. Reported adverse events of hypotension have been mild, non-serious, and have resolved without medical intervention. Both these potential risks will continue to be closely monitored.

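### The Heart Rate Change search in SAP 14.1.1 has no heart-rate increased or decreased term, while the parallel Hypotension search has six blood-pressure-decreased terms

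*SAP*

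**What the plan says.** SAP 14.1.1 sets search criteria for the adverse events of special interest. For heart rate, the list begins "TEAEs of Heart Rate Change are identified as PT: Atrial tachycardia, Postural orthostatic tachycardia syndrome, Rebound tachycardia, Sinus tachycardia" and continues "Supraventricular tachycardia, Tachycardia, Tachycardia paroxysmal, Ventricular tachycardia, Bradycardia". It closes with a full stop and carries no redaction mark; the redaction nearby follows the Hypersensitivity item. The list feeds one output: "Incidence and exposure-adjusted event rates of Heart Rate Change TEAEs by SOC and PT".

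For hypotension, the same section gives "TEAEs are identified as PT: Blood pressure ambulatory decreased, Blood pressure decreased, Blood pressure diastolic decreased, Blood pressure orthostatic decreased", followed by "Blood pressure systolic decreased, Blood pressure systolic inspiratory decreased, Diastolic hypotension, Hypotension, Orthostatic hypotension". A further list of events suggestive of hypotension is made up of symptoms and related events: "Fatigue, Nausea, Loss of consciousness, Vision blurred, Cold sweat, Dizziness, Syncope, Presyncope".

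On the risk itself, Protocol 7.4.2.2 states: "The most important potential risks identified to date include hypotension (and complications related to hypotension and/or tachycardia", and it adds anti-drug antibodies as another such risk.

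Two other parts of the plan bear on the point. SAP 14.1.1 also tabulates every TEAE by PT, by SOC, and by SOC and PT with severity, and gives incidence and exposure-adjusted rates for all TEAEs by SOC and PT. SAP 14.3 summarises pre-dose heart rate and its change to several post-dose time points, with dot plots for Days 1 and 2.

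**The concern.** The two lists cover neighbouring haemodynamic topics but follow different rules. Hypotension takes in both the diagnosis and the measurement finding. Heart Rate Change takes in diagnoses only, although its title names a measurement. The SAP does not say that this was intended.

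Reports of heart-rate findings are foreseeable. Under Protocol 9.10.4.4.1, heart rate is read with every blood pressure: every 15 minutes for two hours and every 30 minutes to four hours on Days 1 to 4, then hourly to eight hours on Days 1 and 2. The Grade 1 definition in Protocol 10.2.3.2 covers purely diagnostic observations. Under Protocol 10.3.1, the sponsor assigns the PT from the term that the site entered.

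Safety and tolerability is the primary objective. The Heart Rate Change table is the only listed output that pools heart-rate adverse events into one topic with incidence and exposure-adjusted rates. A reader who sets it beside the Hypotension table would be comparing searches of different breadth without being told so.

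**Working it through.** **Step 1: count the terms in each list (SAP 14.1.1).**

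| List | PTs | Diagnosis-type terms | Measurement-type terms |
|---|---|---|---|
| Heart Rate Change | 9 | 9 (8 tachycardia, 1 bradycardia) | 0 |
| Hypotension | 9 | 3 (hypotension) | 6 (blood pressure decreased, in six forms) |

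No Heart Rate Change term contains the words heart rate, increased or decreased. The six measurement terms under Hypotension include the unqualified one, as in "Blood pressure ambulatory decreased, Blood pressure decreased, Blood pressure diastolic decreased".

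**Step 2: follow one event through the outputs.** Suppose a TEAE is coded to a heart-rate increased term.

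- Heart Rate Change table: left out, because the PT is not on the list.
- All-TEAE tables by PT and by SOC and PT, including the one with exposure-adjusted rates: present as its own row.
- Vital-sign summaries (SAP 14.3): the underlying reading contributes if it was taken at a summarised time point.

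The loss is therefore confined to the pooled special-interest table.

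**Step 3: effect on incidence.** SAP 14.1 defines incidence as children with the event divided by children in the population. One omission changes it only if the child has no other event on the list; the change is then 1/n.

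- Cohort of 8: 1/8 = 12.5 percentage points.
- Cohort of 10: 1/10 = 10 percentage points.
- All cohorts combined, at the planned total of about 36: 1/36 = 2.8 percentage points.
- The 15 µg/kg dose level, which can hold Cohorts 1 to 3 once Cohorts 1 and 2 have switched (SAP 2.2 and 3.2): at most 8 + 8 + 10 = 26 children, so 1/26 = 3.8 percentage points.

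**Step 4: effect on the exposure-adjusted rate.** SAP 14.1 puts total events, not children, over total exposure. Each omitted event therefore lowers this rate, whether or not the child has another listed event. If every child completes the initial six months:

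- 8 children: 8 × 0.5 = 4 years, so 1/4 = 0.25 events per year of exposure.
- 10 children: 10 × 0.5 = 5 years, so 1/5 = 0.20 events per year of exposure.

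The documents give no count of heart-rate measurement reports, so the total effect cannot be computed. Its sign is known: leaving terms out can only lower the counts.

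**The case against.** The strongest reply is that nothing is lost from the study report. The all-TEAE tables show such an event by name, one of them with the same two statistics, and Protocol 13.4 lists all adverse events. Measured heart rate is summarised directly, and mild findings picked up by monitoring would show there. This stands. A reader might infer that these events go uncounted altogether; the documents do not support that.

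Second, Protocol 10.1.1 and 10.3.1.1 ask sites to record a diagnosis where possible. That favours tachycardia, which is listed. Protocol 9.10.4 also speaks of clinically significant vital-sign changes, not of every reading. So measurement-type reports cannot be called likely, only possible. They were considered possible enough for blood pressure to put six such terms in that list.

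Third, no decision depends on this table. The stopping criteria in Protocol 9.1.1.1 use adverse event grade, hypotension events, QTc-F, ventricular tachycardia and skeletal findings, not the search list. This also stands, and it limits the stakes to reporting.

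Three further readings go beyond the documents:

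- That the Hypotension list holds every blood-pressure-decreased term. SAP 14.1 names MedDRA 19.1, which is not supplied, so only the six printed terms can be confirmed.
- That sinus bradycardia or palpitations must be added. Nothing in the documents shows how these would be coded or that they belong to the topic.
- That postural dizziness is missing from the suggestive list because Phase 1 events occurred on standing. Protocol 7.4.2.1 says that most of those cases had no symptoms, and orthostatic hypotension is already a listed term.

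**Conclusion.** The point holds as an inconsistency between two parallel search lists. Following the SAP as written would leave a heart-rate TEAE coded to a measurement term out of the only pooled table for a risk that the protocol names as important. The incidence shift per affected child is 10 to 12.5 percentage points within a cohort and about 2.8 points overall. The total may be zero.

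This rests on two assumptions:

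- A plain-word report of a raised or lowered heart rate codes to its own PT and not to Tachycardia or Bradycardia. The documents do not show this; the separate blood-pressure-decreased and hypotension terms support it by analogy.
- For the incidence figures, the child has no other event on the Heart Rate Change list.

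The issue concerns the completeness of one table. It does not affect trial conduct, any stopping rule or any test.

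**What to change.** Add the heart-rate increased and heart-rate decreased measurement terms, as worded in MedDRA 19.1, to the Heart Rate Change list in SAP 14.1.1. If the omission was deliberate, state the reason in the SAP and in a footnote to the table.

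Before lock, screen all coded PTs in the study database against the Heart Rate Change and Hypotension lists for other heart-rate or blood-pressure terms that neither list catches. Any further additions would then rest on the study's own coding.

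The cost is one line in the SAP and a small re-run of the affected outputs. Counts in the special-interest table can only stay the same or rise.
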